### 10.6.2. Criteria for Permanent Discontinuation of Trial Intervention (Potential Hy's Law Cases)

The following criteria may suggest the presence of severe liver injury regardless of the etiology; "Hy's law" points to advanced and potentially severe DILI when other possible causes of liver injury have been excluded. When all of the following criteria are met, the IMP should be permanently discontinued and not restarted under any condition and the event should be reported as an SAE.

1. ALT increases to  $\geq 3 \times \text{ULN}$

- 2. Total bilirubin increases to  $\geq 2 \times \text{ULN}$  or  $\text{INR} > 1.5$
- 3. Alkaline phosphatase value  $< 2 \times \text{ULN}$  (ie, absence of significant cholestasis)
- 4. No alternative cause explains the combination of the above laboratory abnormalities; important alternative causes are included in [Table 19](#).

**10.6.3. Criteria for Temporary Withholding or Permanent Discontinuation of Trial Intervention**

Participants who develop abnormal results in liver tests (AST, ALT, alkaline phosphatase, total bilirubin) during the trial treatment period may meet the criteria for discontinuation of IMP treatment specified in the FDA guidance ([Table 18](#)).

**Table 18: Criteria for Temporarily Withholding IMP in Association With Abnormalities in Liver Test Results**

Baseline ALT Value	ALT Elevation
$< 3 \times \text{ULN}$	

<math>> 8 \times \text{ULN}</math>

<math>> 5 \times \text{ULN}</math> for more than 2 weeks

<math>\geq 3 \times \text{ULN}</math> and (total bilirubin <math>\geq 2 \times \text{ULN}</math> or <math>\text{INR} > 1.5</math>)

<math>\geq 3 \times \text{ULN}</math> with the presence of signs and symptoms consistent with acute hepatitis and/or eosinophilia (<math>\geq 500</math> eosinophils/<math>\mu\text{L}</math>)

Abbreviations: ALT=alanine aminotransferase; IMP=investigational medicinal product; INR=international normalized ratio; ULN=upper limit of normal.

IMP should be withheld pending an investigation ([Table 20](#)) of alternative causes of abnormalities in liver test results ([Table 19](#)). Clinical and laboratory follow-up should continue during the withholding period until the abnormalities in liver test results return to baseline values.

Resumption of IMP can only occur with the express consent of the sponsor and/or their medical designee and only if another cause for the abnormal results is identified and liver tests return to within the normal range.

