## **6.5. Dose Modification**

No dose modifications are permitted during the trial.

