### **7.1. Discontinuation of Trial Intervention**

For QTcF, liver enzymes, and/or hematological abnormalities meeting AESI criteria as described in [Section 8.3.7](#), a repeat evaluation should be immediately performed for confirmation and the medical monitor notified.

If the repeat evaluation is confirmed abnormal, the treatment with study drug should be discontinued and the early termination visit should be completed.

If a participant permanently discontinues IMP, refer to the Schedule of Assessments ([Section 1.3](#)) for data to be collected following IMP discontinuation.

If a participant discontinues IMP due to an AE, the investigator or other trial personnel will make every effort to follow the event until it has resolved or stabilized.

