### **7.2. Participant Discontinuation/Withdrawal From the Trial**

All participants have the right to withdraw from the trial at any time without prejudice. Participants cannot withdraw consent for use of data already collected as part of the trial, but can withdraw consent for future participation. The investigator can also discontinue a participant from the trial at any time for safety, behavioral, or compliance reasons. Unless a participant provides written withdrawal of consent or there is other written documentation by the investigator confirming the participant's verbal intent to completely withdraw from the trial, participants should be followed for all protocol-specified evaluations and assessments, if possible.

At the time of discontinuation from the trial, if possible, an early termination visit should be conducted. Unless a participant withdraws consent, an Early Termination Visit and end of trial procedures should be conducted if a participant discontinues IMP. Unless clinically necessary, the initiation of any prohibited medications should occur after the completion of all of the assessments at the Early Termination Visit and Telephone Visits 7 and 8. See the Schedule of Assessments ([Section 1.3](#)) for data to be collected at the time of discontinuation and follow-up and for any further evaluations that need to be completed.

The reason for discontinuation from the trial will be recorded in the eCRF.

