### 8.3.7. Adverse Events of Special Interest

All AESIs should be reported according to the procedures and timelines for SAEs (see [Section 10.3.4](#)).

The following events will be reported as AESIs:

- AEs that result in the discontinuation of IMP
- AEs potentially related to abuse (refer to the Abuse Potential Monitoring Plan [APMP] document for details)
- AEs of suicidality
- C-SSRS (Since Last Visit) "Yes" answer to Suicidal Ideation Items #4 or #5 or any Suicidal Behaviors
- QTcF >500 ms or an increase >60 ms from Baseline
- Liver enzymes:
  - ALT or AST  $\geq 3 \times$  ULN and serum bilirubin  $\geq 2 \times$  ULN (suspected Hy's Law)
  - ALT  $\geq 5 \times$  ULN
- Hematologic abnormalities:
  - Absolute neutrophil count  $< 1.5 \times 10^9/L$
  - Platelet count  $< 100 \times 10^9/L$
  - Hemoglobin  $< 10$  g/dL

For QTcF, liver enzymes, and/or hematological abnormalities meeting the above AESI criteria, a repeat evaluation should be immediately performed for confirmation and the medical monitor notified. See [Section 10.6.1](#) for further details on the assessment of elevations in liver test results.

If the repeat evaluation is confirmed abnormal, the treatment with study drug should be discontinued and the early termination visit should be completed.

An APMP will be used to monitor events that may suggest that darigabat produces drug effects that could be sought out for abuse purposes. As part of the APMP, AEs potentially related to abuse and medication handling irregularities related to suspected or known abuse of IMP must be reported as AESIs. Investigators and site staff at each trial site will be trained on reporting potentially abuse-related AEs. While the investigators will be provided with examples of AE

terms as a guide during trial conduct, the analysis of potentially abuse-related AEs will be based on a search by the sponsor of all relevant MedDRA terms, all verbatim terms, and any open text fields within the AE data to identify text strings suggestive of abuse potential, consistent with US FDA guidance ([US FDA Guidance for Industry, 2017](#)).

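### Protocol 7.1 and 8.3.7 end treatment for confirmed liver results that 10.6.3 (Table 18) only withholds for or does not list, and no section says which rule governs

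*Protocol*

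**What the plan says.** Protocol 8.3.7 lists two liver criteria among the adverse events of special interest: ALT or AST of at least 3×ULN together with bilirubin of at least 2×ULN, and ALT of at least 5×ULN. Either one calls for an immediate repeat and notice to the medical monitor. Then: "If the repeat evaluation is confirmed abnormal, the treatment with study drug should be discontinued and the early termination visit should be completed". Protocol 7.1 repeats the rule: "the treatment with study drug should be discontinued and the early termination visit should be completed". Section 7.2 adds, unless consent is withdrawn, that "an Early Termination Visit and end of trial procedures should be conducted if a participant discontinues IMP".

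Section 10.6.3 contains Table 18, titled "Criteria for Temporarily Withholding IMP in Association With Abnormalities in Liver Test Results". For a baseline ALT below 3×ULN its triggers are:

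- ALT above 8×ULN;
- ALT above 5×ULN for more than 2 weeks;
- ALT of at least 3×ULN with bilirubin of at least 2×ULN or INR above 1.5;
- ALT of at least 3×ULN with signs and symptoms of acute hepatitis and/or eosinophilia.

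The action is to withhold IMP during an investigation. After that, "Resumption of IMP can only occur with the express consent of the sponsor and/or their medical designee", and only if another cause is identified and liver tests are back in the normal range.

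**The concern.** Both rules apply to practically every dosed participant. Table 18 has one row, for baseline ALT below 3×ULN, and exclusion criterion 11 keeps out anyone with ALT or AST of 2×ULN or more at Screening. A site that follows 7.1 ends treatment on a confirmed result. A site that follows 10.6.3 may withhold and later restart, or may find no trigger at all.

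The first issue is consistent handling of a safety signal. The second is reporting. SAP 5.8 counts treatment discontinuations with reasons, and SAP 5.17.1 summarises events leading to discontinuation of IMP. SAP 5.11.1 and 5.12.1.1 treat discontinuation as an intercurrent event, with data used only through the discontinuation visit. SAP 5.12.2.1 uses only data from before discontinuation. A participant who is terminated and one who is withheld and then resumes are therefore counted differently and contribute different lengths of follow-up.

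**Working it through.** No arithmetic applies. The check is to put the same confirmed liver result through each rule. The inputs are the triggers set out above and the four conditions of Protocol 10.6.2: ALT at least 3×ULN; bilirubin at least 2×ULN or INR above 1.5; alkaline phosphatase below 2×ULN; no alternative cause. Isolated means that no bilirubin, INR, hepatitis or eosinophilia criterion is met.

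| Confirmed result | 7.1 and 8.3.7 | 10.6.3, Table 18 | 10.6.2 |
|---|---|---|---|
| (a) ALT 9×ULN, isolated | Discontinue, ET visit | Withhold, restart possible | Not met |
| (b) ALT 6×ULN for 3 days, isolated | Discontinue, ET visit | No trigger listed | Not met |
| (c) ALT 6×ULN for more than 2 weeks, isolated | Discontinue, ET visit | Withhold, restart possible | Not met |
| (d) ALT 3.5×ULN, bilirubin 2.5×ULN, another cause found | Discontinue, ET visit | Withhold, restart possible | Not met |
| (e) As (d), no other cause, alkaline phosphatase below 2×ULN | Discontinue, ET visit | Withhold, restart condition cannot be met | Permanent discontinuation |

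The results separate into three groups.

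1. In (a), (c) and (d) both rules stop dosing. They differ on what follows. Sections 7.1 and 8.3.7 have no duration condition, no exception for an alternative cause and no restart route. Section 10.6.3 has a restart route, open only if another cause is found.
2. In (b) the rules differ on whether any action on IMP is triggered. The same holds for any isolated ALT from 5×ULN up to and including 8×ULN that lasts 2 weeks or less.
3. In (e) every rule leads to no further dosing, so there is no practical conflict.

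Table 18 itself shows that the two rules were not written to work together. A criterion of ALT above 5×ULN for more than 2 weeks is useful only if a participant can remain on drug at that level for 2 weeks. Under 7.1 and 8.3.7 an immediate repeat would already have ended treatment.

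Nothing in the documents ranks the rules. Section 8.3.7 refers to 10.6.1 for liver assessment, but not to 10.6.3. Section 10.6.3 is also inconsistent in its labels: its heading covers both temporary withholding and permanent discontinuation, its lead-in speaks of discontinuation, and its table title speaks of temporary withholding. The amendment history in 10.9 records that Version 2.0 added the stopping rules to 7.1 and 8.3.7, and neither summary of changes lists a revision of 10.6. That may be how the mismatch arose, but this is inference.

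**The case against.** The best defence is that 10.6 is headed as suggested actions, so 7.1 and 8.3.7 might be taken to prevail. Table 18 also lists only reasons to withhold, so its silence at 5 to 8×ULN is not an instruction to continue. Central oversight narrows the scope for sites to diverge: 10.6.1 requires the medical monitor to be consulted from ALT 3×ULN, 7.1 and 8.3.7 require the monitor to be notified, and a restart needs the sponsor's consent. All of this is fair and reduces the likely frequency of the problem. It does not remove it, because the monitor and sponsor have no precedence rule either, and a restart route has no place beside a rule that requires the early termination visit.

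One could also read withholding as the interim step until the repeat result arrives. That cannot explain a trigger defined by more than 2 weeks of elevation.

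Several stronger readings are tempting, and the documents do not support them:

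- **Opposite actions throughout.** Where a Table 18 trigger also meets 8.3.7, both rules stop dosing. They part on termination and restart.
- **10.6.2 contradicts 10.6.3.** Section 10.6.2 says "When all of the following criteria are met, the IMP should be permanently discontinued", and one of its criteria is that no alternative cause explains the results. Section 10.6.3 allows a restart only if such a cause is found. The two can run in sequence.
- **6.5 forbids withholding.** It says "No dose modifications are permitted during the trial", but 8.3.6 names interruptions and modifications as separate things.
- **The lack of an AST trigger in 10.6.2 and Table 18 is an error.** Section 10.6.1 gives a reason for relying on ALT, and 8.3.7 still covers AST with bilirubin.
- **AESI counts depend on the rule a site applied.** The liver thresholds for AESIs are in 8.3.7 and are repeated unchanged in SAP 3.2.1.1. A qualifying laboratory result is an AESI whether the site stops or withholds. The fold-ULN tables in SAP 5.17.3 likewise come from laboratory values.

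**Conclusion.** The inconsistency is real and confined to 7.1 and 8.3.7 against 10.6.3. It covers two groups of results. In the first (ALT above 8×ULN, ALT above 5×ULN for more than 2 weeks, or ALT at least 3×ULN with bilirubin at least 2×ULN), the rules differ on termination versus possible restart. The restart difference takes effect only when another cause is identified and tests normalise. In the second (isolated, asymptomatic ALT of 5 to 8×ULN for 2 weeks or less), they differ on whether any action on IMP is triggered.

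The consequences fall on participant handling and on the number and timing of IMP discontinuations. How many participants are affected cannot be learned from the documents and may be none. The conclusion assumes that the discontinuation in 7.1 and 8.3.7 is final. Neither uses the word permanent in the liver rule, but the early termination visit and the end-of-trial procedures in 7.2 leave no way back.

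The SAP introduction and SAP section 6 say that the study closed after a February 2025 decision and that ongoing participants stopped treatment early. Reporting is therefore the part that can still be acted on.

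**What to change.** Reconcile Protocol 7.1, 8.3.7 and 10.6.3 into one consistent set of triggers and actions, and state which section governs. With dosing over, this serves mainly as a clarification for the record and for any later protocol that reuses the text. The choice of threshold or action belongs to the sponsor.

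For the CSR, add one listing of every participant who met any liver trigger in 8.3.7 or Table 18. Show the dates and values, whether a repeat confirmed the result, whether another cause was found, and the action on IMP: stopped, withheld, resumed or continued. The planned hepatic tables cannot stand in for it: SAP 5.17.3 cuts ALT at 3, 5, 10 and 20×ULN, with no 8×ULN cut and no action on IMP. If the listing is empty, one sentence in the CSR settles the matter. The cost is short clarification wording and one listing, which should need only laboratory, AE and dosing data already collected.

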#### 10.6.4. Evaluation of Alternative Causes of Liver Test Result Abnormalities

**Table 19: Alternative Causes of Abnormalities in Liver Test Results**

Biliary obstruction, focal liver lesions (benign or malignant), vascular liver disease (such as portal vein thrombosis or Budd-Chiari syndrome)
Viral hepatitis (eg, hepatitis A/B/C/D/E, Epstein-Barr virus, cytomegalovirus, herpes simplex virus, varicella, toxoplasmosis, and parvovirus)
Autoimmune hepatitis
Exposure to hepatotoxic agents/drugs or hepatotoxins (other than IMP), including herbal and dietary supplements, plants, and mushrooms
Alcoholic hepatitis
Nonalcoholic steatohepatitis and hepatic steatosis
Congestive heart failure, hypotension, ischemic hepatitis
Others: sepsis, sinusoidal obstruction syndrome, primary biliary cholangitis, primary sclerosing cholangitis, Wilson disease, hemochromatosis, alpha-1-antitrypsin deficiency

Abbreviations: IMP=investigational medicinal product.

**Table 20: Investigation of Alternative Etiologies for Elevated Liver Test Results**

Initial set of tests a	
Complementary Tests and Parameters	Etiologies
Complete blood count with differential (eg, eosinophilia)	Infection (sepsis), immune-related DILI (eosinophilia), high MCV (alcoholic hepatitis)
ALT, AST, GGT, serum PETH	Alcoholic hepatitis (AST:ALT ratio $\geq 2$ )
ALP and GGT	Biliary obstruction
CPK, haptoglobin, LDH, and peripheral blood smear	Rhabdomyolysis and hemolysis
HAV IgM	Hepatitis A
HBsAg, anti-HBc IgM, total anti-HBc, anti-HBs, HBV-DNA (by PCR)	Hepatitis B (acute, reactivation of chronic or occult hepatitis B)
anti-HCV, HCV-RNA (by PCR)	Acute hepatitis C
HEV IgM and IgG	Acute hepatitis E
Liver imaging (ultrasound, CT, or MRI)	Biliary obstruction, focal lesions, vascular liver disease, hepatic steatosis
Serum total IgG, ANA, anti-smooth muscle antibody	Autoimmune hepatitis
Serum acetaminophen (paracetamol) concentration	Acetaminophen (paracetamol) overdose

**Obtain a more detailed history as follows:**

- Prior and concurrent diseases or illness
- Exposure to environmental and/or industrial chemical agents
- Presence of symptoms (if applicable) including right upper quadrant pain, hypersensitivity-type reactions, fatigue, nausea, vomiting, and fever
- Prior and concurrent alcohol use, recreational drug use, and special diets
- Concomitant use of medications (including nonprescription medicines and herbal and dietary supplements), plants, and mushrooms

**Additional set of testsb**

Complementary Tests and Parameters	Etiologies
Echocardiogram	Congestive heart failure
CMV IgM (CMV-DNA)	Acute CMV infection
EBV IgM (EBV-DNA)	Acute EBV infection
HSV IgM (HSV-DNA)	Acute HSV infection
Anti-mitochondrial autoantibodies	PBC
24 hours urine copper and serum ceruloplasmin	Wilson disease
Iron studies (serum iron and ferritin) and transferrin saturation	Hemochromatosis
Serum alpha-1 antitrypsin	Alpha-1-antitrypsin deficiency
MRI, ERCP, ANA, perinuclear anti-neutrophil cytoplasmic	PSC

**Hepatology consult may be requested (a liver biopsy may be considered in consultation with a hepatologist). The medical monitor should be contacted for questions regarding adequate follow up tests.**

Abbreviations: ALP=alkaline phosphatase; ALT=alanine aminotransferase; ANA=anti-nuclear antibody; anti-HBc=hepatitis B core antibody; anti-HBs=hepatitis B surface antibody; anti-HCV=hepatitis C virus antibody; AST=aspartate aminotransferase; CMV=cytomegalovirus; CPK=creatinine phosphokinase; CT=computed tomography; DILI= drug-induced liver injury; DNA=deoxyribonucleic acid; EBV=Epstein Barr virus; ERCP=endoscopic retrograde cholangiopancreatography; GGT=gamma glutamyltransferase; HAV=hepatitis A virus; HBsAg=hepatitis B surface antigen; HBV=hepatitis B virus; HCV=hepatitis C virus; HEV=hepatitis E virus; HSV=herpes simplex virus; Ig=immunoglobulin; LDH=lactate dehydrogenase; MCV=mean corpuscular volume; MRI=magnetic resonance imaging; PBC=primary biliary cholangitis; PCR=polymerase chain reaction; PEth=phosphatidylethanol; PSC=primary sclerosing cholangitis; RNA=ribonucleic acid.

a To be done for all participants.

b To be done when clinically indicated.

## 10.7. Moderate to Strong Inducers and Inhibitors of Cytochrome P450 3A4 (not exhaustive)

Note that this may not be a complete list and that the investigator is responsible for ensuring that participants are not receiving any moderate to strong inducers or moderate to strong inhibitors of cytochrome P450 3A4 during the trial.

CYP 3A4 Inhibitors	CYP 3A4 Inducers
HIV antivirals	HIV antivirals
Indinavir	Efavirenz
Nelfinavir	Nevirapine
Ritonavir	Etravirine
Saquinavir	Miscellaneous
Boceprevir	Barbiturates
Lopinavir/ritonavir	Carbamazepine
Amprenavir	Cenobamate
Atazanavir	Eslicarbazepine
Telaprevir	Glucocorticoids (systemic)
Darunavir/ritonavir	Modafinil
Fosamprenavir	Oxcarbazepine d
Antibiotics	Phenobarbital
Clarithromycin	Phenytoin
Erythromycin	Pioglitazone
Telithromycin	Rifabutin
Ciprofloxacin	Rifampin
Anti-infectives	St. John's wort
Itraconazole	Troglitazone
Ketoconazole	Bosentan
Fluconazole	Nafcillin
Posaconazole	Avasimibe
Voriconazole	
Anti-anginal therapy	
Diltiazem	
Verapamil	
Anti-cancer therapy	
Crizotinib	
Imatinib	
Miscellaneous	
Nefazodone	
Aprepitant	
Grapefruit juice a,b	
Conivaptan	
Mibefradil c	

Abbreviations: CYP=cytochrome P450; HIV=human immunodeficiency virus.

- a The effect of grapefruit juice varies widely among brands and is concentration-, dose-, and preparation dependent. Studies have shown that it can be classified as a “strong CYP3A4 inhibitor” when a certain preparation was used (eg, high dose, double strength) or as a “moderate CYP3A4 inhibitor” when another preparation was used (eg, low dose, single strength).
- b A 7-day washout prior to dosing is required if grapefruit juice was being consumed continually.
- c Withdrawn from the United States market.
- d Doses >900 mg/day.

## 10.8. Abbreviations

Abbreviation	Definition
AE	adverse event
AESI	adverse event of special interest
ALT	alanine aminotransferase
APMP	Abuse Potential Monitoring Plan
AST	aspartate aminotransferase
BID	twice daily
BMI	body mass index
BZD	benzodiazepine
CFR	Code of Federal Regulations
CGI-S	Clinical Global Impression-Severity of Symptoms Scale
CI	confidence interval
CKD-EPI	Chronic Kidney Disease Epidemiology Collaboration
CNS	central nervous system
CO 2	carbon dioxide
CRF	case report form
CSR	clinical study report
C-SSRS	Columbia-Suicide Severity Rating Scale
DILI	drug-induced liver injury
DSM-IV	Diagnostic and Statistical Manual of Mental Disorders, Fourth Edition
DSM-5-TR	Diagnostic and Statistical Manual of Mental Disorders, Fifth Edition, Text Revision
ECG	electrocardiogram
eCRF	electronic case report form
eGFR	estimated glomerular filtration rate
EQ-5D-5L	European Quality of Life
FDA	Food and Drug Administration
FSH	follicle-stimulating hormone
GABA A	gamma-amino-butyric-acid type A
GAD	generalized anxiety disorder
HAM-A	Hamilton Anxiety Scale
IB	Investigator's Brochure
ICE	intercurrent event

Abbreviation	Definition
ICF	informed consent form
IEC	Independent Ethics Committee
IMP	investigational medicinal product
INR	international normalized ratio
IRB	Institutional Review Board
IRT	Interactive Response Technology
MedDRA	Medical Dictionary for Regulatory Activities
MINI	Mini International Neuropsychiatric Interview
MMRM	mixed model for repeated measures
NCI-CTCAE	National Cancer Institute- Common Terminology Criteria for Adverse Events
PAM	positive allosteric modulator
PD	pharmacodynamics
PDSS	Panic Disorder Severity Scale
PK	pharmacokinetic
PSL-IV	Panic Symptom List-IV
PWC	Physician Withdrawal Checklist
QTcF	QT interval corrected for heart rate using Fridericia's formula
RO	receptor occupancy
SAE	serious adverse event
SAP	Statistical Analysis Plan
SDS	Sheehan Disability Scale
SNRI	serotonin and norepinephrine reuptake inhibitors
SPV	saccadic peak velocity
SSRI	selective serotonin reuptake inhibitors
TEAE	treatment-emergent adverse event
THC	tetrahydrocannabinol
TIA	transient ischemic attack
ULN	upper limit of normal
VAS	visual analog scale
WOCBP	woman of childbearing potential

